- Subjects that are 3 weeks to 6 months post liver transplant will be screened for the study. After eligibility is established and informed consent document has been signed by the patient or representative, subjects will be randomized to spironolactone 25 mg daily, or no treatment. Non-English only speaking subjects will be consented with an interpreter. A total of 36 patients will be randomized (50/50), 18 to treatment and 18 to standard of care. Subjects that do not wish to enroll or do not meet the criteria for the main study may choose to participate in the sub-study if they are not allergic to iodine and if their GFR is greater than 30 ml/min. 36 subjects may be enrolled in the sub-study to compare the currently used method of evaluating kidney function based on serum creatinine to other measures of creatinine clearance and kidney filtration rate (iothalamate GFR, 24 hour urine for creatinine clearance and protein, serum cystatin C, basic metabolic package and serum albumin).

Inclusion Criteria

- Liver transplant within 3 weeks to 6 months of study enrollment.
- Age 18-75 years old
- Proteinuria less than 3 g/24 hours
- Creatinine Clearance greater than 30 ml/min
- Negative pregnancy test for women of child bearing potential

Exclusion Criteria

- Patients on angiotensin converting inhibitors or angiotensin receptor blockers, digoxin, other drugs associated with hyperkalemia (dapsone can be substituted for sulfamethoxazole if needed at the discretion of the investigator)
- Potassium greater than 5.2 meq/L on screening labs, one occasion in a non-hemolyzed specimen,
- Prior intolerance to spironolactone
- Factors, that in the opinion of the investigator, would interfere with subject's compliance with the study
- Retransplantation
- Combined organ transplant-i.e. liver kidney, liver-heart
- Subjects who are anticipated to be placed on sirolimus or everolimus due to underlying condition (i.e. patients with HCC outside Milan criteria or with vascular invasion). Other

renal sparing protocols are allowed in including initial treatment with simulect, CNI reduction with mycophenolate mofetil

- Allergic to iodine

Patients will be monitored by SOC transplant protocol for up to 2 years.

For those subjects on treatment, if potassium stays less than 5.2 meq/L after 1 month on treatment, spironolactone may be increased to 50 mg daily at the discretion of the investigator.

4. Statistical analysis:

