Mean GFR will be compared using unpaired Students' T test between groups and paired Students' t test within groups. If creatinine clearance is not normally distributed a nonparametric test will be used (Wilcoxon rank sum test) to compare creatinine clearance between groups. Sample size: 16 subjects in each group will be needed to detect a 10 ml difference in creatinine clearance with a power of 0.5 at $p \leq 0.05$.

5. Outcomes:

Primary outcome

- Change in creatinine clearance from screening to 1 year post randomization based on iothalamate GFR (glomerular filtration rate).
- Renal function tests will be compared to the iothalamate GFR to determine which best approximates the Glofil results.

Secondary outcomes

- Patient survival
- Graft Survival
- 6 month and 18 month creatinine clearance
- Dialysis
- Hyperkalemia ($>5.5 \text{ mEq/L}$)
- Proteinuria as defined by $> 3 \text{ g/24h}$

- Discontinuation for adverse events
- Conversion to renal sparing immunosuppressive regimen
- Number of subjects requiring sodium bicarbonate (NaHCO₃)
- Calculation of CKD-EPI, CKD-EPI Cystatin, CKD-EPI-Cystatin-Creatinine, MDRD-4, MDRD-6 and 24 hour urine creatinine clearance at screening and 6, 12, 18, and 24 months. Comparison of the currently used method of evaluating kidney function based on serum creatinine to other measures of creatinine clearance and kidney filtration rate (CKD-EPI, CKD-EPI Cystatin, CKD-EPI-Cystatin-Creatinine, MDRD-4, MDRD-6, 24 hour urine creatinine clearance and iothalamate GFR).

6. Study Calendar of Events

	Screening	Randomization	Day 7	Wk 2	Wk 3	Wk 4	MONTHLY until month 24	MONTHS 6,12,18,24
	45 days from screening	±2 days	±2 days	±2 days	±2 days	±5 days	±2 weeks	
History and physical	X							
Vitals signs (if recorded as part of the standard of care visit)	X	X	X	X	X	X	X	
ECG	X							
CHEM-7	X	X	X	X	X	X*		
Albumin level (standard of care lab within 30 days)	X						X	
24 HR creatinine clearance and 24 hour urine protein							X	
Cystatin C		X						X

		[name]					
		ONLY 12, 24 MONTHS					
Iothalimate GFR **		X					
Adverse events		X					
BLOOD FOR DNA ANALYSIS (Preferably collected at randomization, but may be collected at any post-randomization visit)		X					

*BMP weekly for 2 weeks if dose change in spironolactone or addition of NaHCO₃

**Depending in the budget a subset of subjects may undergo iothalimate scans at baseline and 1 year

7. Safety and Monitoring Plan

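### The primary change in iothalamate GFR is to be tested without a baseline covariate; ANCOVA on the scan the endpoint already needs, with a baseline-adjusted fallback, would be a near-free gain in precision

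*Combined protocol and SAP*

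**What the plan says.** Section 5 (Primary outcome) defines the endpoint as "Change in creatinine clearance from screening to 1 year post randomization based on iothalamate GFR".

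Section 4 gives the tests: "Mean GFR will be compared using unpaired Students' T test between groups and paired Students' t test within groups". It does not say whether these, or the rank-based fallback it names for non-normal data, are applied to the change or to the 1-year level. The fallback is worded as follows: "a nonparametric test will be used (Wilcoxon rank sum test) to compare creatinine clearance between groups". The wording may be kept general because Section 5 also lists a secondary outcome, "6 month and 18 month creatinine clearance". No adjusted model is mentioned in any section.

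The sample size statement in Section 4 is "16 subjects in each group will be needed to detect a 10 ml difference in creatinine clearance with a power of 0.5" at the 0.05 level, with no SD, correlation or sidedness. Section 3 states: "A total of 36 patients will be randomized (50/50), 18 to treatment and 18 to standard of care". A footnote to the calendar in Section 6 adds: "Depending in the budget a subset of subjects may undergo iothalimate scans at baseline and 1 year".

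**The concern.** On the ordinary reading, the t-test is run on change. Baseline then enters only by subtraction, which fixes its slope at 1. Section 3 says: "Subjects that are 3 weeks to 6 months post liver transplant will be screened for the study". Kidney function may still be settling to different degrees across that window, so neither a slope of 1 nor equal SDs at the two times can be taken for granted. ANCOVA estimates the slope and is generally more precise. Precision is scarce when the plan's own power is 0.5.

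The fallback raises a second issue. As worded, it compares creatinine clearance, not change, and a normality check triggers it. It could therefore move the primary comparison from change to 1-year level after the data are seen. Where baseline and 1-year values are well correlated, a test on level discards much of the information.

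**Working it through.** **Inputs from the document.** Section 4: 16 per arm, 10 ml difference, power 0.5, level 0.05. Section 3: 18 per arm randomized. **Assumed:** two-sided test, SD, baseline/1-year correlation r, and the ratio k of 1-year SD to baseline SD.

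**1. The plan's own figure.** Without an SD, 16 per arm cannot be reproduced, so I solved for the SD. Noncentral t power with 30 df equals 0.5 at SD = 13.97 (16.8 if one-sided). Check: standard error = 13.97 × √(2/16) = 4.94 ml; critical t = 2.042; 95% CI half-width = 2.042 × 4.94 = 10.09 ml, about the size of the target difference, as power near one half requires.

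**2. ANCOVA with equal SDs at both times.** Let V be the variance of a single measurement.
- Variance of change = 2(1 − r)V.
- ANCOVA residual variance = (1 − r²)V = [(1 + r)/2] × variance of change.
- ANCOVA has 2n − 3 df, and estimating the slope inflates the variance by 1 + 1/(2n − 4), which is 1 + 1/28 = 1.036 at n = 16.

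Example at r = 0.5, taking 13.97 as the SD of change: residual SD = 13.97 × √0.75 = 12.10; standard error = 12.10 × √(2/16 × 1.036) = 4.35; half-width = 2.045 × 4.35 = 8.90 ml; power 0.603.

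| r | Change t-test | ANCOVA | Gain (points) | Gain if 13.97 is the SD of level |
|---|---|---|---|---|
| 0.3 | 0.500 | 0.665 | 16.5 | 14.2 |
| 0.5 | 0.500 | 0.603 | 10.3 | 10.3 |
| 0.6 | 0.500 | 0.576 | 7.6 | 8.0 |
| 0.7 | 0.500 | 0.550 | 5.0 | 5.3 |
| 0.8 | 0.500 | 0.527 | 2.7 | 2.1 |
| 0.9 | 0.500 | 0.505 | 0.5 | 0.1 |

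The half-width falls from 10.09 ml to 8.90, 9.19, 9.48 and 9.75 ml at r = 0.5, 0.6, 0.7 and 0.8. With 18 per arm, power is 0.550 for change and 0.659 to 0.581 for ANCOVA over the same range. The two tests have equal power at r = 0.927 (16 per arm) or 0.936 (18 per arm).

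**3. Unequal SDs.** ANCOVA residual variance = k²(1 − r²)/(1 + k² − 2rk) × variance of change. With the SD of change held at 13.97, 16 per arm and r = 0.5, 0.6, 0.7, 0.8:
- k = 0.75: power 0.761, 0.742, 0.729, 0.730 (gain 23 to 26 points).
- k = 1.25: power 0.530, 0.509, 0.493, 0.486 (+3 to −1 points).

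The residual variance can never exceed the variance of change; the two are equal when the true slope rk is 1. Power is then 0.486, so the largest possible loss is 0.500 − 0.486 = 1.4 points.

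**4. Scans in a subset.** If only 8 per arm were scanned (an illustration), power would be 0.266 for change and 0.313 to 0.269 for ANCOVA at r = 0.5 to 0.8.

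**5. Fallback, by simulation.** 16 per arm, 10 ml effect, SD of change 13.97, equal SDs; 6,000 trials per setting (4,000 with 999 permutations for permutation ANCOVA).

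| Test | Normal, r = 0.5, 0.6, 0.7, 0.8 | Heavy tails (t, 3 df), r = 0.5 and 0.8 |
|---|---|---|
| Wilcoxon on level | 0.47, 0.39, 0.30, 0.21 | 0.67 and 0.33–0.34 |
| Wilcoxon on change | 0.47 throughout | 0.67 and 0.69 |
| Rank ANCOVA | 0.57, 0.53, 0.50, 0.45 | see below |
| Permutation ANCOVA | 0.59 at 0.5, 0.53 at 0.8 | 0.70 and 0.64 |

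A separate heavy-tailed simulation gave rank ANCOVA 0.80 and 0.72 against 0.72 and 0.72 for Wilcoxon on change. The Wilcoxon figures differ from those in the table, so absolute power depends on how the heavy tails are generated. With no effect, rejection rates in the tabulated simulations lay between 0.038 and 0.054.

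**The case against.** The strongest reply is that nothing here is wrong. The change t-test is valid under randomization, and since Section 5 defines the outcome as change, baseline is already used by subtraction. The gain rests on inputs that the document does not supply. At r = 0.7 to 0.8 with equal SDs it is 5.0 to 2.7 points, or 3.0 to 1.6 if the SD of change is 20. It is zero or slightly negative at k = 1.5 with r = 0.5 to 0.7, and nothing in the document supports the favourable k = 0.75. Power stays near 0.53 to 0.60 at 16 per arm. All of this stands, and it makes the point an improvement in precision, not a correction.

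On the fallback, simply stating that the Wilcoxon test applies to change would remove the large loss seen on level, and that test also keeps the Section 5 outcome. This stands in part. An adjusted fallback is not always the most powerful: at r = 0.8, permutation ANCOVA has 0.64 against 0.69 with heavy tails, and rank ANCOVA 0.45 against 0.47 with normal data. Rank ANCOVA also gives no difference in ml. The argument for an adjusted fallback is that it tests the same baseline-adjusted comparison as the primary analysis.

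Finally, the Section 6 footnote means the baseline scan is not assured for everyone. True, but a subject without both scans cannot contribute a change score either, so this limits both analyses alike.

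**Conclusion.** The point holds as a recommended improvement. Section 4 plans no baseline adjustment for a primary outcome that already requires the baseline measurement. With equal SDs at both times and 16 per arm, ANCOVA adds about 2 to 10 power points at correlations of 0.5 to 0.8, about 14 to 17 at 0.3, and essentially nothing from 0.9 up. With unequal SDs the range is wider: 23 to 26 points when the 1-year SD is 0.75 times baseline, +3 to −1 when it is 1.25 times. The loss is bounded at about 1.4 points. All these figures rest on an SD back-solved from the plan's stated power, a two-sided 0.05 test and assumed correlations.

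The fallback matters most if it is run on 1-year level, which the wording allows: its power would drop to 0.21 at a correlation of 0.8 with normal data. ANCOVA does not resolve the stated power of 0.5 or the missing SD.

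**What to change.** In Section 4, state that the primary analysis of the Section 5 outcome is ANCOVA of 1-year iothalamate GFR on assigned arm, with screening (baseline) iothalamate GFR as covariate, reported as the adjusted difference with its 95% CI. Modelling change with the same covariate gives the same treatment estimate and p-value, because subtracting baseline only shifts the baseline coefficient by 1. The endpoint therefore need not be redefined.

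Replace the Wilcoxon fallback with a permutation test of the ANCOVA arm effect, permuting labels as the randomization allows, or with rank ANCOVA. Run it as a prespecified sensitivity analysis whatever the normality check shows.

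A minor separate edit: report within-group changes descriptively. The plan does not say the paired tests will serve as evidence of effect, but comparing two within-group p-values does not test spironolactone.

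The cost is a few sentences and one degree of freedom, at most about 1.4 power points at 16 per arm. No data are needed beyond the two scans that the change endpoint already requires.

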**Carolinas HealthCare System
Center for Liver Disease**

Spironolactone to prevent or delay calcineurin nephrotoxicity after liver transplantation

Title: Investigator initiated study of spironolactone to prevent or delay calcineurin nephrotoxicity in liver transplant recipients

Principal Investigator: [name]

Sub-Investigators:

[name]
[name]
[name], MD
[name], PA-C
[name], PA-C
[name]
[name]
[name]
[name]

1. Specific Aim:

- a. To determine if spironolactone decreases nephrotoxicity from calcineurin inhibitors in liver transplant recipients.
- b. To determine the best study of renal function in liver transplant recipients.

2. Background:

Chronic kidney injury affects up to 30% of liver transplant recipients after transplantation.

Nephrotoxicity from calcineurin inhibitors (CNIs- tacrolimus, cyclosporine) is the leading cause of chronic kidney injury after liver transplantation. Strategies to reduced kidney injury include minimizing exposure to CNI's by using combination immunosuppressive regimens, such as low dose CNI and mycophenolate mofetil. Other strategies include switching from CNI to Mammalian target of rapamycin (mTOR) inhibitor. However, there may be barriers to using low dose CNI or mTOR inhibitor such as increased rate of rejection, CMV infection, or increased cost. Spironolactone is an antagonist of aldosterone, acting primarily through competitive binding of receptors at the aldosterone-dependent sodium-potassium exchange site in the distal convoluted renal tubule. Animal models of CNI nephrotoxicity demonstrate decreased nephrotoxicity and kidney fibrosis in rodents treated with spironolactone. Small studies have demonstrated improved creatinine clearance in liver transplant recipients treated with spironolactone. In these studies spironolactone at low doses was well tolerated with acceptable rates of hyperkalemia.

3. Study design:

Randomized clinical trial of spironolactone versus no spironolactone in liver transplant recipients on calcineurin inhibitors (tacrolimus or cyclosporine).

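### Section 4 fixes neither the primary variable nor the primary between-group test before the data are seen; the switch itself inflates error little, but it changes what is estimated

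*Combined protocol and SAP*

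**What the plan says.** Section 4 (Statistical analysis) gives the default: "Mean GFR will be compared using unpaired Students' T test between groups and paired Students' t test within groups". The next sentence makes the between-group test conditional: "If creatinine clearance is not normally distributed a nonparametric test will be used (Wilcoxon rank sum test"), and applies the fallback to creatinine clearance. Nothing says how normality is judged, at what threshold, on levels or changes, pooled or by arm, or by someone unaware of allocation.

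The same section sizes the trial on a mean difference: "16 subjects in each group will be needed to detect a 10 ml difference in creatinine clearance with a power of 0.5". Section 3 randomizes 18 patients to each arm.

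Section 5 (Outcomes) words the primary outcome as "Change in creatinine clearance from screening to 1 year post randomization based on iothalamate GFR (glomerular filtration rate"), which ties the two terms together. Its secondary outcomes nevertheless list 24-hour urine creatinine clearance and iothalamate GFR as different measures. A footnote to the Section 6 calendar says that, depending on budget, only a subset may have iothalamate scans.

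**The concern.** A test chosen by looking at the outcome data is not a pre-specified test. The fallback is named but the rule for invoking it is not, so two competent analysts could reach different primary tests from the same data. The control arm is untreated and the documents describe no masking, so nothing shields that judgement from knowledge of the results.

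The two tests also answer different questions. The t test concerns a difference in means in ml. The rank sum test concerns whether values in one arm tend to exceed those in the other, and gives no estimate of the 10 ml difference. If the switch fires, the primary result no longer addresses the planned quantity.

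The change of term adds a second open choice. If iothalamate is available only in a subset, 24-hour creatinine clearance becomes a natural substitute, and the text does not clearly exclude it.

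**Working it through.** **1. The plan's own figure.** Inputs from Section 4: n = 16 per group, difference 10 ml, power 0.5, p ≤ 0.05. No SD or sidedness is given, so 16 cannot be reproduced, only inverted. From n = 2(z_α + z_power)²·SD²/Δ², with z_power = 0 at power 0.5, SD = Δ·√(n/2)/z_α.
- Two-sided: 10 × √8 / 1.96 = 14.4 ml (14.0 with the t distribution).
- One-sided: 10 × √8 / 1.645 = 17.2 ml (16.8 with the t distribution).

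On any of these readings the design quantity is a mean difference in ml.

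**2. How the check behaves.** The plan names no normality test, so I assume Shapiro-Wilk at 0.05 in each arm.
- With truly normal data, at least one arm triggers the switch with probability 1 − 0.95² = 9.75%. Simulation gave about 9% to 10%.
- With lognormal-type skew (log-SD 0.6), the check missed the skew in 46% to 47% of arms of 16. It missed both arms in about 0.46² = 21% of trials.

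**3. Error of the switch when both arms share one distribution.** This is the null in which treatment does nothing. Assumptions: two-sided 5%; n = 16 and 18 per arm; normal, t with 3 df, lognormal (log-SD 0.5 and 1), exponential and uniform data; 40,000 trials per setting (standard error about 0.11 points).
- Shapiro-Wilk on pooled data, on residuals or in either arm: 4.6% to 5.5%.
- Worst case: 5.5% (lognormal 0.5, n = 18, residual or either-arm check), 0.5 points above nominal.
- At 18 per arm and 100,000 trials: residual check 5.2% (normal) and 5.3% (lognormal 0.5); pooled check 5.0% and 4.8%; t test fixed in advance 5.0% and 4.8%; rank sum fixed in advance 4.7% in both.

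**4. Error when the arms differ in shape or spread but not in mean.** These scenarios are assumptions; the documents give no such figures. Ranges are over repeated simulation runs. At 12,000 trials the standard error near 6.6% is √(0.066 × 0.934 / 12,000) = 0.23 points.

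| Assumed scenario | Switch | Rank sum, fixed | Student t, fixed | Welch t, fixed |
|---|---|---|---|---|
| One arm left-skewed, equal SDs, 16 v 16 | 6.4–6.9% | 6.5–6.6% | 5.8% | 5.2–5.3% |
| Both left-skewed, SD 1.5 times larger in the smaller arm, 13 v 18 | 9.1–9.8% | 8.4–8.7% | 6.7–6.8% | 5.9–6.0% |

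Within the same run, switch minus fixed rank sum was 6.9 − 6.6 = 0.3 and 6.4 − 6.5 = −0.1 points in the first scenario. In the second it was 9.2 − 8.7 = 0.5 and 9.1 − 8.4 = 0.7 points. Most of the excess therefore belongs to the rank sum and Student tests under unequal shapes or spreads. Reversing the second scenario, so that the larger arm has the larger SD, gave 6.9%.

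**5. Error if choices are free.** Equal arms sharing one distribution.
- Better of the two tests, one measure: 5.3% to 6.4%.
- Best of two tests on two measures: from 8.3% (correlation 0.9) to 11.1% (correlation 0.5). The correlations are assumed.

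**The case against.** The strongest reply has four parts.

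First, the fallback is named in advance, and a normality-triggered switch costs little when the arms share one distribution. That stands, and it sets the size of the error-rate point.

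Second, if spironolactone has no effect at all, randomization gives both arms one distribution. An arm-specific skew or a 1.5-fold SD ratio implies that treatment or differential loss has altered the distribution, so calling every rank sum rejection a type I error is loose. That also stands. Unequal loss is plausible, because the Section 8 potassium rules remove only treated subjects, but neither 13 v 18 nor an SD ratio of 1.5 is in the documents.

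Third, a reader might infer that the plan lets the analyst report whichever p value is smaller. It does not: the only stated ground for switching is non-normality, and choosing by p value would breach the rule. The figures for free choice show what an undefined trigger fails to prevent, not what the plan permits.

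Fourth, a reader might infer that normality is checked on a different variable from the one tested. The documents do not establish this, since Section 5 defines one term through the other. A check on another variable would not by itself raise the error either. What remains is an ambiguity about the endpoint, made material by the separate listing of the two measures and by the iothalamate footnote.

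None of this supplies the missing decision rule or the missing single variable.

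**Conclusion.** The point holds in a limited form. Section 4 leaves the primary test to an undefined look at the data and does not use one name for the primary variable. The main consequence is for what is estimated: a switch abandons the ml difference on which the trial is sized, and an arm-wise check would trigger it in about one normal-data trial in ten.

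The documents do not support the inference that the switch itself drives the error rate towards 10%. Under a formal Shapiro-Wilk check at 0.05, with both arms sharing one distribution, the excess is about 0.5 points or less. The 6% to 10% figures rest on assumed differences in shape or spread and arise mostly from the tests themselves. The larger exposure, about 8% to 11%, requires a free choice of measure as well as test and rests on assumed correlations of 0.9 to 0.5. All these figures assume two-sided testing, which the plan does not state.

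**What to change.** In Section 4:
- Name the change in iothalamate GFR from screening to 1 year as the single primary variable, and use that term throughout.
- Analyse it by one pre-specified model adjusted for screening GFR, reporting the mean difference in ml with a 95% CI and standard errors that allow unequal variances.
- Delete the normality-dependent switch.
- Always report the rank sum test, with a Hodges-Lehmann interval, as a named sensitivity analysis.

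The drafting cost is about two sentences, and the screening value is already needed for a change endpoint. The calendar footnote allowing scans in only a subset must be reconciled with iothalamate GFR as the primary variable.

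The statistical cost is some power if changes are strongly skewed. In simulation an unadjusted t test had about 0.56 against 0.71 for the rank sum test, at a shift giving the t test 0.51 under normality. That matters in a trial planned at power 0.5. Baseline adjustment may offset part of the loss, and the sensitivity analysis would show it.

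### 24-hour creatinine clearance is planned at screening and four follow-up visits, but the named arm comparison covers only months 6 and 18, with no stated method or baseline adjustment

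*Combined protocol and SAP*

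**What the plan says.** **Section 5, secondary outcomes.** Two bullets concern creatinine clearance.

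- The first reads in full "6 month and 18 month creatinine clearance". It names no instrument and does not say whether the outcome is a level or a change.
- The second lists several estimating equations together with "24 hour urine creatinine clearance at screening and 6, 12, 18, and 24 months". Its next sentence gives the use: "Comparison of the currently used method of evaluating kidney function based on serum creatinine to other measures of creatinine clearance and kidney filtration rate". Arms are not mentioned.

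**Section 5, primary outcome.** This is the change from screening to one year, measured by iothalamate GFR.

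**Section 4.** Mean GFR is compared by an unpaired t test between groups and a paired t test within groups. A rank-sum test compares creatinine clearance between groups if the data are not normal. No visit is named and no covariate is mentioned.

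**Section 6, calendar.** The row "24 HR creatinine clearance and 24 hour urine protein" carries one mark in the extracted text, in a follow-up column, and none under Screening or Randomization.

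**Section 3, inclusion criteria.** Entry requires "Proteinuria less than 3 g/24 hours" and a creatinine clearance above 30 ml/min, the latter without a stated method.

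**The concern.** The title speaks of preventing or delaying nephrotoxicity, and Section 3 follows patients for up to two years. No filtration outcome is explicitly compared between arms at month 24, although Section 5 has the 24-hour clearance calculated then. At month 12 the only named arm comparison is by iothalamate, and the calendar footnote allows those scans to be limited to a subset if the budget requires. Patients without a scan would have a 12-month urine clearance that no arm comparison uses.

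Precision is also at stake. Section 4 accepts a power of 0.5, so the trial has none to spare. An unadjusted comparison of levels ignores a screening value that Section 5 already calls for. If the calendar really omits the screening collection and a site works from the calendar alone, that value may never be obtained, and it cannot be recovered after randomisation.

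**Working it through.** **1. Time points, side by side.**

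| Visit | 24-hour clearance planned (Section 5) | Filtration outcome named for comparing arms |
|---|---|---|
| Screening | yes | baseline for iothalamate change only |
| Month 6 | yes | clearance, method and baseline not stated |
| Month 12 | yes | iothalamate change (primary) |
| Month 18 | yes | clearance, method and baseline not stated |
| Month 24 | yes | none |

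If the 6- and 18-month bullet means the 24-hour urine, 2 of the 4 follow-up urine values reach a named arm comparison.

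**2. The plan's own figure.** Section 4 gives 16 per group for a 10 ml difference, power 0.5 and p ≤ 0.05, but no standard deviation, so the figure cannot be reproduced. It can be solved backwards. With n = 2(1.96 + 0)²SD²/10² and n = 16 (two-sided, normal approximation), SD = 10 × √8 / 1.96 = 14.43 ml. Whether Section 4 had a level or a change in mind is not stated.

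**3. Variance under three analyses.** Assume equal variance σ² at baseline and follow-up, with correlation r (not given in the documents).

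- Follow-up level: σ².
- Change score: 2(1 − r)σ², a reduction of 2r − 1.
- Baseline adjustment (ANCOVA): (1 − r²)σ², a reduction of r².

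| r | Change score removes | Adjustment removes |
|---|---|---|
| 0.6 | 2(0.6) − 1 = 20% | 0.6² = 36% |
| 0.8 | 2(0.8) − 1 = 60% | 0.8² = 64% |

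At r = 0.5 the change score gains nothing. At r = 0.3 its variance is 2 × 0.7 = 1.4 times that of the level.

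**4. What this means for power.** Illustration with 18 per arm, a 10 ml difference and two-sided 0.05, from the noncentral t distribution. The single degree of freedom spent on the covariate is ignored.

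| Assumed SD | Assumed r | Level | Change score | Adjusted |
|---|---|---|---|---|
| 14.43 | 0.3 | 0.52 | 0.40 | 0.56 |
| 14.43 | 0.5 | 0.52 | 0.52 | 0.65 |
| 14.43 | 0.7 | 0.52 | 0.74 | 0.81 |
| 20 | 0.3 | 0.31 | 0.23 | 0.33 |
| 20 | 0.5 | 0.31 | 0.31 | 0.39 |
| 20 | 0.7 | 0.31 | 0.47 | 0.53 |

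In every row adjustment gives the highest power of the three.

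**5. The calendar.** As extracted, the albumin and cystatin C rows each keep a baseline and a follow-up mark, while the 24-hour urine row has one. If cells only shifted, one mark still cannot serve both times; if a mark was lost, the row shows nothing. The iothalamate row also has one mark, although its footnote describes scans at baseline and one year, so counting marks in this table is not safe.

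**The case against.** The strongest reply is that the plan excludes nothing. Section 5 does schedule the urine clearance at screening and all four follow-ups. Section 4 compares clearance between groups without restricting visits, and its paired tests use a baseline. The sentence that schedules the calculations is separate from the sentence about comparing methods, so the 12- and 24-month values are not expressly reserved for that purpose. All of this stands. What remains is that no between-arm use of those values is stated, and a paired test within each group does not compare the arms.

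Several stronger readings are tempting, and the documents do not support them:

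- *The 24-hour clearance is named only at months 6 and 18, and so can give no change score.* Section 5 lists screening and four follow-ups.
- *The calendar proves that no baseline urine is collected.* The table is visibly damaged, and the proteinuria criterion requires a protein result before randomisation whatever the row shows. The clearance criterion names no method, so it proves nothing either way.
- *The arms are never compared on change with one instrument.* The primary outcome does exactly that at one year, by iothalamate.
- *A 24-month iothalamate value goes unused between arms.* This depends on which row the note "ONLY 12, 24 MONTHS" belongs to, which cannot be read; the footnote mentions only baseline and one year.

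**Conclusion.** The point holds as a gap in specification and a missed gain in precision, not as a missing measurement. The 6- and 18-month outcome lacks a method and a baseline, the 12- and 24-month urine clearances have no stated arm comparison, and the screening urine value adjusts none. Under an assumed r of 0.6 to 0.8, adjustment would remove 36% to 64% of the variance of a follow-up level. That range rests on the assumed correlation and on a linear relation between baseline and follow-up; the change-score and power figures also assume equal variances, and the power figures an assumed SD. The direction does not depend on the exact r: apart from the one degree of freedom for the covariate, adjustment is no less precise than the level or the change score. The calendar discrepancy is conditional on the original table. The primary outcome is untouched.

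**What to change.** 1. Check the original calendar. If the screening mark is absent, mark the 24-hour urine (creatinine clearance and protein) at Screening, to agree with Sections 3 and 5.
2. Replace the 6- and 18-month bullet with: *24-hour urine creatinine clearance at 6, 12, 18 and 24 months, compared between arms with adjustment for the screening value (ANCOVA or a repeated-measures model).* Add the same analysis to Section 4. Adjustment is preferable to a plain change score, which loses precision if r is below 0.5.
3. Report this series separately from iothalamate GFR, so that values from two instruments are not read as one course.

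The cost is wording and a little analysis. Section 5 already requires all five collections, so no visit or test is added to what it plans.
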